1.2 Number of Digits to be Displayed

Term	Definition
Percentage (%)	Incidence of AE or ADR, etc.: Displayed to two decimal places by rounding Other: Displayed to one decimal place by rounding
Summary statistics	Mean, median, first quartile, and third quartile: Displayed to one lower digit than raw data by rounding Standard deviation: Displayed to two lower digits than raw data by rounding Minimum and maximum: Displayed to the same number of digits as raw data
P-value	P-value will be displayed to three decimal places by rounding down. P-value rounded down to less than 0.001 will be displayed as p<0.001.

1.3 Level of Significance, Confidence Coefficient

Level of significance: 5% (two-sided test)

Confidence coefficient: 95% (two-sided estimate)

1.4 Handling of Test/Measurement Data

Test/measurement data will be handled in accordance with the criteria described below (with 1 month as 30 days). If there are multiple pieces of data at the same specified time point, data on the test day closest to the specified day of assessment will be employed, and the latest data among different pieces of data on different days with the same deviation from the specified day of assessment will be

employed. At the final assessment*, values measured on the day closest to the start date of treatment with Zacro + 374 days will be employed. Values measured 15 days or more after the end day of treatment with Zacro will not be employed.

The number of days from the start day of treatment with Zacro is 1 day for the start day of treatment with Zacro and -1 day for the previous day.

* After 12 months of treatment with Zacro (or at discontinuation of treatment with Zacro)

Time point of test	Permissible range (number of days from the start day of treatment)	Specified day of assessment
At the start of treatment	-90 to 1	Start date of treatment
After 1 month of treatment	2 to 45	Start date of treatment + 30
After 2 months of treatment	46 to 75	Start date of treatment + 60
After 3 months of treatment	76 to 105	Start date of treatment + 90
After 4 months of treatment	106 to 135	Start date of treatment + 120
After 5 months of treatment	136 to 165	Start date of treatment + 150
After 6 months of treatment	166 to 195	Start date of treatment + 180
After 7 months of treatment	196 to 225	Start date of treatment + 210
After 8 months of treatment	226 to 255	Start date of treatment + 240
After 9 months of treatment	256 to 285	Start date of treatment + 270
After 10 months of treatment	286 to 315	Start date of treatment + 300
After 11 months of treatment	316 to 345	Start date of treatment + 330
After 12 months of treatment	346 to 375	Start date of treatment + 360
At the final assessment	2 to 375	Start date of treatment + 374

2.0 Disposition of Patients (Patient Composition Diagram)

(1) Patients included in tabulation/analysis

Enrolled patients

(2) Data tabulated/analyzed

The number of enrolled patients, number of medical institutions involved in patient registration, number of patients from whom the CRF is collected, number of patients from whom the CRF is not collected, number of finalized patients, number of non-finalized patients, number of patients included in safety evaluation, number of patients excluded from safety evaluation, number of patients included in efficacy evaluation, and number of patients excluded from efficacy evaluation will be tabulated.

For the number of medical institutions involved in patient registration, one medical institution with different departments should not be counted more than once.

For patients from whom the CRF is not collected, the number of patients by reason for failure to collect will be tabulated.

For patients excluded from safety evaluation and those excluded from efficacy evaluation, the number of patients by reason for exclusion will be tabulated, and excluded patients will be listed.

Patients meeting any of the criteria listed below will be handled as described below regarding whether to employ them or not.

Criterion	Safety evaluation	Efficacy evaluation
Prescription before the contract period [posterior finding]	×	×
Registration 15 days or more after prescription of Zacras [posterior finding]	×	×
Non-target disease	○	×
Deviation from exclusion criteria	○	×
Failure to confirm the intake of Zacras [after the patient enrollment period]	×	×
Unavailability of follow-up CRF	○	○
It is unknown whether the patient experienced an AE	×	×

○: employed, ×: excluded or not employed

(3) Table/figure number

Figure 2.0-1, Table 2.0-1

Disposition (multiple tabulation)*	ACE inhibitor, ARB, diuretic (thiazide and thiazide analogue diuretic), Ca antagonist, direct renin inhibitor, aldosterone antagonist, potassium-sparing diuretic, fixed-dose combination: ARB + diuretic, fixed-dose combination: ARB + Ca antagonist, fixed-dose combination: ARB + Ca antagonist + diuretic, fixed-dose combination: Ca antagonist + statin, other
Antihypertensive other than Zembrin: treatment with HCTZ (during the survey period)	No, yes
Disposition	6.25 mg, 12.5 mg, other
Treatment with antihypertensive other than Zembrin (within 2 months before the start of treatment with Zembrin)	No, yes
Disposition (multiple tabulation)*	ACE inhibitor, ARB, diuretic (thiazide and thiazide analogue diuretic), Ca antagonist, direct renin inhibitor, aldosterone antagonist, potassium-sparing diuretic, fixed-dose combination: ARB + diuretic,

	fixed-dose combination: ARB + Ca antagonist, fixed-dose combination: ARB + Ca antagonist + diuretic, fixed-dose combination: Ca antagonist + statin, other
Number of concomitant drugs (antihypertensive other than Zpras)	
(at the start of treatment with Zpras)	0, 1, 2, 3, 4, 5, ≥ 6
(at the end of treatment with Zpras)	0, 1, 2, 3, 4, 5, ≥ 6
Concomitant non-antihypertensive drug (during the survey period)	No, yes
Disposition (multiple tabulation)	Antidiabetic, antidyslipidemic, antihyperuricemic, other

* For fixed-dose combinations, individual ingredients will be tabulated separately. If “fixed-dose combination: ARB + diuretic” is used concomitantly, for instance, “ARB” and “diuretic” will also be tabulated.

(3) Table/figure number

Table 4.0-1

5.0 Tabulation/Analysis of Safety

5.1 Occurrence of Adverse Events and Adverse Drug Reactions/Infections

5.1.1 Occurrence of Adverse Events

(1) Patients included in tabulation/analysis

Patients included in safety evaluation

(2) Data tabulated/analyzed

The following variables will be tabulated:

Variable	Data tabulated/analyzed
Number of patients with an AE	Number of patients who experienced an AE
Number of AE	Number of reported AE. Multiple episodes of the same AE (PT) in the same patient will be tabulated as the total number of episodes.
Incidence of AE	The incidence of AE will be calculated as number of patients with an AE/number of patients included in safety evaluation × 100.
Type of AE	AEs will be classified by SOC and then tabulated by PT. For laboratory tests, AEs will be classified by SOC, then sorted by HLGT, and finally tabulated by PT. For SOC, the number of patients with an AE and the incidence of AE will be listed by SOC internationally agreed order. For PT, the number of patients with an AE and the incidence of AE will be listed in ascending order of PT code. Multiple episodes of the same AE (PT) in the same patient will be tabulated as 1 patient.

(3) Table/figure number

Table 5.1-1

5.1.2 Occurrence of Adverse Drug Reactions/Infections

(1) Patients included in tabulation/analysis

Patients included in safety evaluation

(2) Data tabulated/analyzed

The following variables will be tabulated:

Variable	Data tabulated/analyzed
Number of patients with an ADR, etc.	Number of patients who experienced an ADR, etc.
Number of ADR, etc.	Number of reported ADR, etc. Multiple episodes of the same ADR, etc. (PT) in the same patient will be tabulated as the total number of episodes.
Incidence of ADR, etc.	The incidence of ADR, etc. will be calculated as number of patients

	with an ADR, etc./number of patients included in safety evaluation $\times 100$.
Type of ADR, etc.	
ADRs, etc. will be classified by SOC and then tabulated by PT. For laboratory tests, ADRs, etc. will be classified by SOC, then sorted by HLGT, and finally tabulated by PT.
 
For SOC, the number of patients with an ADR, etc. and the incidence of ADR, etc. will be listed by SOC internationally agreed order.
 
For PT, the number of patients with ADR, etc. and the incidence of ADR, etc. will be listed in ascending order of PT code. Multiple episodes of the same ADR, etc. (PT) in the same patient will be tabulated as 1 patient.

(3) Table/figure number

Table 5.1-2

5.2 Occurrence of Adverse Events and Adverse Drug Reactions/Infections in Patients Excluded from Safety Evaluation

5.2.1 Occurrence of Adverse Events

(1) Patients included in tabulation/analysis

Patients excluded from safety evaluation

(2) Data tabulated/analyzed

The following variables will be tabulated:

Variable	Data tabulated/analyzed
Number of patients with an AE	Number of patients who experienced an AE
Number of AE	Number of reported AE. Multiple episodes of the same AE (PT) in the same patient will be tabulated as the total number of episodes.
Incidence of AE	The incidence of AE will be calculated as number of patients with an AE/number of patients excluded from safety evaluation $\times 100$.
Type of AE	
AEs will be classified by SOC and then tabulated by PT. For laboratory tests, AEs will be classified by SOC, then sorted by HLGT, and finally tabulated by PT.
 
For SOC, the number of patients with an AE and the incidence of AE will be listed by SOC internationally agreed order.
 
For PT, the number of patients with an AE and the incidence of AE will be listed in ascending order of PT code. Multiple episodes of the same AE (PT) in the same patient will be tabulated as 1 patient.

(3) Table/figure number

Table 5.2-1

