7.4 Completion and Submission of Case Report Form

For each of all registered patients, the investigator shall complete and submit a CRF to Takeda Pharmaceutical within approximately 1 month after the end of the observation period. Any failure to confirm the intake of Zacras Combination Tablets shall be specified (no further information is required).

For patients discontinued from treatment with Zacras Combination Tablets for any reason during the observation period, the investigator shall complete and submit a CRF to Takeda Pharmaceutical within approximately 1 month after the end of required observation. For any patient discontinued from treatment with Zacras Combination Tablets due to an adverse event, the investigator shall complete and submit a CRF to Takeda Pharmaceutical after monitoring the patient as long after discontinuation of treatment as possible until the adverse event is confirmed to have resolved or be resolving.

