1.0 Definitions of Terms, etc. and Handling of Test/Measurement Data

1.1 Definitions

Term	Definition
Zacras	Zacras Combination Tablets are abbreviated as Zacras in this document.
SOC	System organ class listed in the MedDRA/J
HLGT	High level group term listed in the MedDRA/J
PT	Preferred term listed in the MedDRA/J
LLT	Lowest level term listed in the MedDRA/J
Enrolled patient	Patient allowed to be enrolled
Patient from whom the CRF is collected	Patient from whom the CRF has been obtained
Patient from whom the CRF is not collected	Enrolled patient from whom the CRF has not been collected
Finalized patient	Patient from whom the CRF is collected who has the date of CRF completion entered into the PMS system or who requires no information on the CRF status and has not been excluded from the survey
Non-finalized patient	Patient from whom the CRF is collected who has not been finalized
Patient included in safety evaluation	Finalized patient who is included in safety evaluation
Patient excluded from safety evaluation	Finalized patient who is excluded from safety evaluation
Patient included in efficacy evaluation	Patient included in safety evaluation who is included in efficacy evaluation
Patient excluded from efficacy evaluation	Patient included in safety evaluation who is excluded from safety evaluation
Presence or absence of change in daily dose of Zacras	“Yes” for patients with a change in daily dose between the start of treatment with Zacras and the final assessment
Duration of treatment with Zacras	End date of treatment with Zacras - start date of treatment with Zacras + 1
End date of treatment	End date of the final dose described in the column of the end date of treatment in the CRF; or start date of treatment + 360 days if the end date of treatment is not described in the CRF and there is a check for “ongoing at 12 months after the start of treatment with Zacras.”
Treatment completer	Patient with a duration of treatment with Zacras of \geq start date of treatment + 360 days
Treatment non-completer	Patient with a duration of treatment with Zacras of \leq start date of treatment +

Term	Definition
	359 days

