5.2.2 Occurrence of Adverse Drug Reactions/Infections

(1) Patients included in tabulation/analysis

Patients excluded from safety evaluation

(2) Data tabulated/analyzed

The following variables will be tabulated:

Variable	Data tabulated/analyzed
Number of patients with an ADR, etc.	Number of patients who experienced an ADR, etc.
Number of ADR, etc.	Number of reported ADR, etc. Multiple episodes of the same ADR, etc. (PT) in the same patient will be tabulated as the total number of episodes.
Incidence of ADR, etc.	The incidence of ADR, etc. will be calculated as number of patients with an ADR, etc./number of patients excluded from safety evaluation × 100.
Type of ADR, etc.	ADRs, etc. will be classified by SOC and then tabulated by PT. For laboratory tests, ADRs, etc. will be classified by SOC, then sorted by HLGT, and finally tabulated by PT. For SOC, the number of patients with an ADR, etc. and the incidence of ADR, etc. will be listed by SOC internationally agreed order. For PT, the number of patients with ADR, etc. and the incidence of ADR, etc. will be listed in ascending order of PT code. Multiple episodes of the same ADR, etc. (PT) in the same patient will be tabulated as 1 patient.

(3) Table/figure number

Table 5.2-2

5.3 Occurrence of Adverse Events and Adverse Drug Reactions/Infections by Seriousness, Time of Onset, and Outcome

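### AE and ADR incidence among patients excluded from safety evaluation (SAP 5.2.1, 5.2.2) counts excluded patients with no AE information as event-free

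*SAP*

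**What the plan says.** References are to the current SAP edition, the first of the three in the file.

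- **Rate for AEs (SAP 5.2.1, Table 5.2-1).** "The incidence of AE will be calculated as number of patients with an AE/number of patients excluded from safety evaluation", times 100. The numerator is given as "Number of patients who experienced an AE".
- **Rate for ADRs (SAP 5.2.2, Table 5.2-2).** Patients "with an ADR, etc./number of patients excluded from safety evaluation", times 100.
- **Who is in the denominator (SAP 1.1).** The excluded set is defined as "Finalized patient who is excluded from safety evaluation", with no condition on AE status. A patient can be finalized without CRF content: the definition of a finalized patient also admits one "who requires no information on the CRF status and has not been excluded from the survey".
- **Why patients are excluded (SAP 2.0).** Four criteria remove a patient from safety evaluation. Two concern timing: the drug was prescribed before the site contract, or registration came too late. The third is "Failure to confirm the intake of Zacras [after the patient enrollment period" (the bracketed qualifier is part of the criterion). The fourth is "It is unknown whether the patient experienced an AE".
- **What is collected when intake is not confirmed (Protocol 7.4).** "Any failure to confirm the intake of Zacras Combination Tablets shall be specified (no further information is required".

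SAP 2.0 also has the exclusion reasons tabulated and the excluded patients listed. Nothing in SAP 5.2 takes the last two groups out of the denominator or shows them separately.

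**The concern.** A proportion with an event is interpretable only if everyone in the denominator could have been seen to have the event. Two of the four exclusion reasons fail that test, one by definition and one by inference. Dividing by all four groups together records *not known* as *no event*.

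The SAP does not reason this way elsewhere. It removes patients with unknown AE status from the main safety rates in 5.1. In 6.1 it treats a patient lacking a blood pressure value as missing when computing the proportion with normal pressure. Only in 5.2 does missing event information count as absence of the event.

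At stake is the reading of Tables 5.2-1 and 5.2-2. They will carry a percentage, to two decimals under SAP 1.2, with the same label as the incidence in Tables 5.1-1 and 5.1-2. A reader who sets the two side by side would compare a rate among patients with known AE status against one diluted by patients without it.

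**Working it through.** The plan states no incidence or count for these tables, so there is no figure to reproduce. The check is algebraic.

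**Notation**

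- E: excluded patients with confirmed intake and known AE status, in practice those excluded for timing alone.
- U: excluded patients with unconfirmed intake or unknown AE status. A patient who also has a timing reason belongs here.
- x: patients recorded with an AE (5.2.1) or an ADR (5.2.2).
- u = U / (E + U).

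**Can a patient in U contribute to x?**

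- *AE status unknown:* no. A patient about whom this is unknown cannot be counted as having experienced an AE.
- *Intake not confirmed:* by inference, no. Protocol 7.4 asks for nothing beyond the fact itself, and the AE definition in Protocol 9.2.5 presupposes that the drug was administered. The SAP does not say outright that an event reported for such a patient would be discarded.

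**Formulas, with all of x coming from E**

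- Printed incidence = x / (E + U)
- Incidence among excluded patients with AE information = x / E
- Ratio = E / (E + U) = 1 − u

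**A 10% rate among patients with AE information**

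| u | Printed value |
|---|---|
| 0.10 | 10% × 0.90 = 9.0% |
| 0.25 | 10% × 0.75 = 7.5% |
| 0.50 | 10% × 0.50 = 5.0% |
| 0.75 | 10% × 0.25 = 2.5% |

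**Assumed counts (none are in the documents)**

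The last column gives the possible incidence in the whole excluded set, from x / (E + U) if nobody in U had an event to (x + U) / (E + U) if everybody did.

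| E | U | x | Printed | x / E | Possible range, whole set |
|---|---|---|---|---|---|
| 20 | 0 | 2 | 2/20 = 10.00% | 10.00% | 10.00% to 10.00% |
| 20 | 5 | 2 | 2/25 = 8.00% | 10.00% | 8.00% to 28.00% |
| 20 | 20 | 2 | 2/40 = 5.00% | 10.00% | 5.00% to 55.00% |
| 10 | 30 | 1 | 1/40 = 2.50% | 10.00% | 2.50% to 77.50% |

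So the printed figure is at or below the rate among patients with AE information, and it is the lowest value compatible with the data for the whole set. It is undistorted when U = 0 or x = 0.

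**The case against.** **Materiality.** These are supplementary tables. The main incidences (5.1), the breakdowns by seriousness, onset and outcome (5.3) and the subgroup tables (5.4) use the included set, and no decision rule depends on 5.2. The raw numbers of patients and events are printed, and 2.0 gives the reasons for exclusion, so a careful reader could approximate the alternative rate. All of this stands and keeps the point small. It does not make a percentage that scores unknown as no event correct.

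**Narrow groups.** Only finalized patients are counted, so uncollected CRFs lie outside the set. A missing follow-up CRF does not exclude a patient from safety evaluation. Unconfirmed intake applies only after the enrollment period. This also stands: u may be small or zero.

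**Internal consistency.** The population and denominator of 5.2.1 and 5.2.2 are the same set, so there is no arithmetic slip. That is right; the issue is how missing AE information is handled. It is also fair that patients who truly took no drug would dilute a whole-set rate without being misclassified. The unknown-status group has no such defence.

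**Stronger readings that the documents do not support**

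- *That the rates are certain to be too low, or low by a large factor.* A reader could assume 40 excluded patients, 25 of them in the two groups, and 3 with an AE: 3/40 = 7.5% printed against 3/15 = 20.0%. That mix is only an assumption, and other mixes give no distortion.
- *That 5.2 exists to show that the exclusions hid no risk, and so gives false reassurance.* The section has a title, a population and a tabulation, but no stated purpose.
- *That the same dilution affects serious events in 5.6.* As written, 5.6.1 and 5.6.2 divide by patients included in safety evaluation. That conflicts with the heading of 5.6, but it is a separate mismatch.

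**Conclusion.** The point holds for SAP 5.2.1 and 5.2.2. The incidence is printed over a set that includes patients with no AE information, and it equals (1 − u) times the incidence among excluded patients who have that information. For unknown AE status this follows from the definition. For unconfirmed intake it rests on the inference from Protocol 7.4 and the AE definition; an event nevertheless recorded for such a patient would alter the exact factor.

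The documents give no counts, so the size cannot be stated beyond the dependence on u, and it may be nil. The calculation also assumes that patients excluded for timing alone have usable AE data, which SAP 2.0 does not say. The result is a modest correction to two supplementary tables. It leaves the main safety results as they are.

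**What to change.** In SAP 5.2.1 and 5.2.2, define the incidence denominator as excluded patients with confirmed intake and known AE status, and state that number in the table. Show the other two groups beneath it as counts labelled *AE status not available*, without a percentage. State that a patient meeting several exclusion criteria goes to the *not available* group if either of these two applies.

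The cost is a few lines of SAP text and a footnote in each table. No new data are needed, because the reason for exclusion is already tabulated under SAP 2.0. The downside is a smaller denominator and so a less stable percentage. Section 5.6 should not be changed on this ground; its denominator conflict needs its own correction.

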5.2.2 Occurrence of Adverse Drug Reactions/Infections

(1) Patients included in tabulation/analysis

Patients excluded from safety evaluation

(2) Data tabulated/analyzed

The following variables will be tabulated:

Variable	Data tabulated/analyzed
Number of patients with an ADR, etc.	Number of patients who experienced an ADR, etc.
Number of ADR, etc.	Number of reported ADR, etc. Multiple episodes of the same ADR, etc. (PT) in the same patient will be tabulated as the total number of episodes.
Incidence of ADR, etc.	The incidence of ADR, etc. will be calculated as number of patients with an ADR, etc./number of patients excluded from safety evaluation × 100.
Type of ADR, etc.	ADRs, etc. will be classified by SOC and then tabulated by PT. For laboratory tests, ADRs, etc. will be classified by SOC, then sorted by HLGT, and finally tabulated by PT. For SOC, the number of patients with an ADR, etc. and the incidence of ADR, etc. will be listed by SOC internationally agreed order. For PT, the number of patients with ADR, etc. and the incidence of ADR, etc. will be listed in ascending order of PT code. Multiple episodes of the same ADR, etc. (PT) in the same patient will be tabulated as 1 patient.

(3) Table/figure number

Table 5.2-2

5.3 Occurrence of Adverse Events and Adverse Drug Reactions/Infections by Seriousness, Time of Onset, and Outcome

